Clinical unit confinement		X	х	x		x		X		x		x						At least 6 hours following study drug administration on dosing days; discharge from the clinical unit will be at the discretion of the investigator provided there are no safety concerns identified from review of the clinical data. Optional overnight confinement from either D -2 or D -1 and on days prior to other dosing days (D7, D14, D21, D28)
Outpatient visit			X											X	X	X	X	If the patient is not overnight confined on D -1 (see above), the D -1 visit will be an outpatient visit
Site to contact patient					х		Х		X		X		X					Investigator or designee to telephone the patient between D2-6, D9-13, D16-20, D23-27, and D30-34
,			/c 23	100			Centi	al L	abora	atory	Asse	ssme	nts	744				
Viral serology (HBsAg, IGM anti-HBc, anti-HCV, HIV) and COVID-19	х																	
Urine alcohol	X		X									X		X				Locally performed at site
Drug screening	X		X	Ĭ.								X		X				

CONFIDENTIAL Page 22 of 101

Protocol TB006AD2102

Protocol Date and Version: 15 Oct 2021; v 3.0

Table 1. Part 1	- Sche	dule	of A	ctivit	ies													
	g -2ª						St	udy I	rug	Adm	inistr	ation	ı Peri	iod				Notes
	Screening D -28 to D -2	D-2ª	D-1ª	D1ª	D2-6ª	D8	D9-13 ^a	D15a	D16-20ª	D22ª	D23-27a	D29a	D30-34ª	D36 a	D64ª	D104ª	E/D ^b	
Clinical laboratory tests (clinical chemistry, hematology, urinalysis)	X		х			x				X				X		X	X	
The second second			Phar	macod	lynai	nic A	Lssess	men	ts: Co	ogniti	on T	estin	g, MI	RI, B	lood	Samp	les	
MMSE	X		X					X				8		X	X	X	X	
Clinical Dementia Rating scale			X					X						X	X	X	X	
Cognitive Drug Research Dementia Rating battery ^d	X		X			X		X		X		X		X	X	X	X	
NPI		-	X											X	X	X	X	
Blood sample for PD assessment	5 - 6		X	e.								1		X		X	X	Fluid biomarkers will be determined in plasma
								Sti	udy T	reati	nent							
Study drug IV infusion				X		X		X		X		X						

CONFIDENTIAL Page 23 of 101

Protocol TB006AD2102

Protocol Date and Version: 15 Oct 2021; v 3.0

Table 1. Part 1	- Sche	dule	of A	ctivit	ies													
	, 2ª						Stu	udy E)rug	Adm	inistr	ation	ı Peri	iod				Notes
	Screening D -28 to D -2a	D-2ª	D-1ª	DIa	D2-6ª	D8	D9-13 ^a	D15a	D16-20ª	D22ª	D23-27a	D29a	D30-34ª	D36 a	D64ª	D104ª	E/D ^b	
								Ph	arma	cokiı	etics		2 25		×			
Blood sample for PK assessment				X	¥. 34	X			5.			X		X	X	X	X	Pre-dose, end of infusion, then 1, 2, 4, and 6 hours after the end of infusion on D1, D8, and D29; single time point on other days

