Blood sample for ApoE4 genotyping	X																	Optional ApoE4 sampling is collected at screening but can be taken at any visit until the last study visit (Section 8.7)
					J	Phar	maco	kinet	ics ar	ıd Ph	arm	acody	ynam	ics				
Blood sample for ADA assessment				X		X								X		X		ADA assessment is performed on blood sample collected for PK assessments; D1 and D8 assessment is performed on the pre-dose sample
Lumbar puncture for CSF collection ^e			х											X				Lumbar puncture indicated for D-1 can be performed any time between D-8 and D-1 CSF biomarkers, and TB006 levels will be determined in CSF

AD = Alzheimer's Disease; ADA = anti-drug antibody; AE = adverse event; anti-HCV = hepatitis C virus antibody; ApoE4 = apolipoprotein E4; COVID = coronavirus disease; CRF = case report form; C-SSRS = Columbia Suicide Severity Rating Scale; CSF = cerebrospinal

fluid; D = Day; DSM-5 = Diagnostic and Statistical Manual of Mental Disorders, Fifth Edition; ECG = electrocardiogram; E/D = Early Discontinuation;

HBsAg = hepatitis B surface antigen; IgM anti-HBc = immunoglobulin M antibody to hepatitis B core antibody; IV = intravenous(ly); MMSE = Mini-Mental State Examination;

NINCDS-ADRDA = National Institute of Neurological and Communicative Disorders and Stroke –

Alzheimer's Disease and Related Disorders Association; NPI = Neuropsychiatric Inventory; PD = pharmacodynamic(s);

PK = pharmacokinetic(s); SAE = serious adverse event.

CONFIDENTIAL Page 24 of 101

a Visit days and procedures are allowed a window of \pm 2 days from Day 1 to End of Treatment.

Protocol TB006AD2102

Protocol Date and Version: 15 Oct 2021; v 3.0

b Applicable only for patients who discontinue early from the study.

- c The medical history assessed at the screening visit should include prior AD treatment assessment(s). Establishing the clinical diagnosis of AD should include use of criteria from the DSM-5 Criteria for Major Neurocognitive Disorder (previously dementia) (Section, 10.4, Appendix 4) and the NINCDS-ADRDA (Note: ADRDA is now the Alzheimer's Association) (Section 10.5, Appendix 5).
- d The Cognitive Drug Research battery is to be performed twice during the screening visit in both Part 1 and Part 2.
- e The lumbar puncture procedure is optional.

f

Protocol TB006AD2102

Protocol Date and Version: 15 Oct 2021; v 3.0

	.2a						St	udy I)rug	Adm	inistr	ation	Peri	iod				Notes

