3 OBJECTIVES AND ENDPOINTS

Table 3. Objectives and Endpoints

O	BJECTIVES - PART 1	ENDPOINTS
Pr	imary	
•	To determine the safety and tolerability of multiple doses of TB006	Safety endpoints, including the incidence of AEs and SAEs, clinical laboratory parameters, vital signs, ECGs, C-SSRS, and physical and neurological examinations, until Day 104 after the first TB006 dosing
•	To determine the PK profile of multiple doses of TB006	 PK parameters derived by noncompartmental analysis using the TB006 plasma concentration-time data, including, but not limited to and as appropriate: AUCtau: area under the concentration-time curve over a dosing interval Cmax: maximum observed plasma concentration tmax: time at which maximum plasma concentration occurs Ctrough: concentration at the end of a dosing interval t½: terminal elimination phase half-life CL: total clearance Vd: volume of distribution Extent of CSF distribution as estimated by TB006 CSF concentrations
•	To determine the maximum tolerated dose of multiple doses of TB006	Safety endpoints as above
•	To assess the immunogenicity of TB006 (production of anti-TB006 antibody)	Detection of anti-TB006 antibodies
•		Change from baseline through end of study on the Clinical Dementia Rating scale – Sum of Boxes total score

Protocol TB006AD2102

Protocol Date and Version: 15 Oct 2021; v 3.0

	 Change from baseline through end of study on the Cognitive Drug Research system battery score, composite scores and individual task measures Change from baseline through end of study on the MMSE score Change from baseline through end of study on the NPI score
--	---

OBJECTIVES - PART 2	ENDPOINTS
Primary	
To determine the clinical efficacy of TB006 in patients with mild to severe AD	Change from baseline through Day 104 on the Clinical Dementia Rating scale – Sum of Boxes total score
Secondary	
To determine the clinical efficacy of TB006 in patients with mild to severe AD	 Change from baseline through Day 36 on the Clinical Dementia Rating scale – Sum of Boxes total score Proportion of responders on the Clinical Dementia Rating scale – Sum of Boxes at Days 36 and 104 Change from baseline to Days 36 and 104 on the Cognitive Drug Research System Battery, composite scores and individual task measures Change from baseline to Days 36 and 104 on the MMSE score Change from baseline to Days 36 and 104 on the NPI score

Protocol TB006AD2102

Protocol Date and Version: 15 Oct 2021; v 3.0

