6.4. PHARMACOKINETIC ENDPOINTS

The PK analysis will be performed using PK parameters derived by non-compartmental analysis (NCA) using the TB006 plasma concentration time data. The PK parameters will be estimated using actual sampling time relative to the start of infusion.

For Part 1 of the study, the PK analysis will be performed as primary endpoint and includes, but not limited to:

- Area under the concentration time curve from time zero to the 6-hour post end of infusion timepoint (AUC₀₋₆) (Days 1, 8, and 29)
- Area under the concentration time curve over a dosing interval (AUC_τ) (Days 1 and 29)
- Area under the concentration-time curve from zero time to the last measurable time point (AUC_{0-*last*}) (Day 29)
- Maximum observed plasma concentration (C_{max}) (Days 1, 8, and 29)
- Time at which maximum plasma concentration occurs (t_{max}) (Days 1, 8, and 29)
- Concentration at the end of a dosing interval (C_{trough}) (Days 8, 15, 22, 29, and 36)
- Terminal elimination phase half-life (t_½) (Day 29 only)
- Total clearance (CL), calculated as dose/AUC_τ. (Day 29 only)
- Volume of distribution (V_d), calculated as dose/kel × AUC_τ, where kel is the apparent elimination rate-constant, computed by log linear regression of the terminal log linear segment of the plasma concentration versus time curve (Day 29 only).

[figure not shown]
The extent of CSF distribution as estimated by TB006 CSF concentrations on Day 36 will also be determined.

For Part 2 of the study, the PK analysis will be performed as secondary endpoint and will include:

- Maximum observed plasma concentration (C_{max}) (Days 1, 8, and 29)
- Concentration at the end of a dosing interval (C_{trough}) (Days 29 and 36)
- Area under the concentration-time curve from zero time to the last measurable time point (AUC_{0-*last*}) (Day 29)
- Terminal elimination phase half-life (t_½) (Day 29 only)

Note that no CSF will be collected in Part 2 of the study.

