9. OVERALL STATISTICAL CONSIDERATIONS

9.1. GENERAL CONVENTIONS

Summary statistics will be presented for categorical data as number and percentage [n (%)] where the percentage is displayed to one decimal point (e.g., 98.1).

Descriptive statistics will be presented for continuous data with applicable decimal precision as follows in relation to the source data (indicated as N), with a maximum of three decimals to be displayed:

- Number (n).
- Mean, (N+1).
- SD, (N+2).
- Median, (N+1).
- Minimum, (N+0).
- Maximum, (N+0).

Study day is calculated relative to the first dose of study drug infusion and will thus in most cases coincide with the visit naming (e.g., Day 1 will be on study day = 1, Day 15 will be on study day = 15 etc.)

- If the current assessment/collection/result (ACR) date is on or after first dose of study drug infusion:

$$\text{Study Day} = (\text{Current ACR Date} - \text{First dose of Study Drug infusion Date}) + 1$$

- If the current ACR date is before first dose of study drug infusion:

$$\text{Study Day} = (\text{Current ACR Date} - \text{First dose of Study Drug Infusion Date})$$

Study day will not be calculated if either the current ACR or the first dose of study drug infusion date is incomplete or missing.

All the tables in Part 1, will be displayed by treatment groups (i.e., TB006 140 mg qw, TB006 420 mg qw, TB006 1000 mg qw, and Pooled placebo).

The dispositions, efficacy, PK/PD, biomarker, and immunogenicity analysis for Part 2 will be classified by treatment groups (i.e., TB006 and Placebo) and baseline AD severity stratifications [i.e. mild AD (MMSE 21-24) and moderate-severe AD (MMSE ≤ 20)]. For efficacy tables of Part 2, the subjects enrolled at the same TB006 dose level in Part 1, as well as all placebo patients will be included.

For all baseline, safety and efficacy assessments, the subjects will be tabulated using the actually received treatment. For example, if there is a subject who is planned to receive TB006 but accidentally gets treated with one of the other regimens, the subject will be tabulated under the other regimen actually received.

The tables and listing for both protocol parts will be presented separately. The detailed layout will be presented in mock shell.

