10.5. PHARMACOKINETICS

The following PK listings are planned for presentation (PKS) for both protocol parts:

- TB006 plasma concentration levels
- TB006 CSF concentration level (Part 1 only)
- Pharmacokinetic parameters of plasma TB006
- Dose-normalized plasma exposure PK parameters (AUCs and C_{max}) – (Part 1 only).

The following descriptive summary tables are planned to be presented for subjects who received TB006 (PKS), by treatment groups and baseline AD severity stratifications (for Part 2 only):

- Plasma concentration of TB006 at each time points
- CSF concentration of TB006 at each time points (Part 1 only)
- Plasma PK parameters
- Dose-normalized exposure PK parameters (AUCs and C_{max}) (Part 1 only, Days 1, 8, and 29, as applicable)
- Power model slope estimate for dose proportionality assessment (including 95% CI) (Part 1 only)

Figures of the following PK items are planned for presentation (PKS) for both protocol parts:

- Overlaid individual plasma concentration versus time plots (linear and semi-logarithmic scale) by treatment groups

- Overlaid mean plasma concentration versus time plots, presented by treatment groups (linear scale with and without SD)
- Overlaid mean plasma concentration versus time plots, presented by treatment groups (semi-logarithmic scale with and without SD)
- Boxplots of dose-normalized PK parameters (AUCs and C_{max}), grouped by treatment groups grouped within each figure (Part 1 only, Days 1, 8, and 29, as applicable)
- Scatterplots of PK parameters (AUCs and C_{max}), versus dose (as part of power model results), by treatment groups (Part 1 only, Days 1, 8 and 29, as applicable)

Assessment of dose proportionality will be performed by PK Day (Day 1, 8, and 29, as applicable) and will not be based strictly on statistical rule criteria but rather, several factors will be taken into account when assessing dose proportionality, such as:

- Power model results (e.g., the slope estimate and the width of the 95% CIs)
- Graphical evaluation (box plots of dose normalized AUCs and C_{max})
- Descriptive statistics by treatment groups of dose-normalized PK parameters

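### Extent of CSF distribution is to be read from the Day 36 CSF concentration, with no measure relative to plasma, although plasma is sampled at the same visit

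*SAP*

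**What the plan says.** Protocol Section 3, Table 3, places this item among the Part 1 primary pharmacokinetic endpoints: "Extent of CSF distribution as estimated by TB006 CSF concentrations". SAP 6.4 fixes the day: "The extent of CSF distribution as estimated by TB006 CSF concentrations on Day 36 will also be determined". Neither sentence has a plasma denominator.

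The planned outputs that involve CSF drug level are:

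- SAP 10.5 lists individual CSF and plasma concentrations, and its descriptive tables by treatment group include "CSF concentration of TB006 at each time points (Part 1 only".
- SAP 9.1 gives the Part 1 table columns as "TB006 140 mg qw, TB006 420 mg qw, TB006 1000 mg qw, and Pooled placebo".
- The pharmacodynamic text that follows the power-model code in SAP 10.5 plans a graphical look at dose, Day 29 plasma AUCtau and Cmax, Day 36 CSF concentration and the biomarkers. The scatter plots it spells out put biomarker change against plasma AUCtau and Cmax.

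Dose normalisation and the power model in SAP 10.5 cover plasma AUCs and Cmax, not CSF.

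On sampling, Protocol Table 1 notes for the Day 36 lumbar puncture: "CSF biomarkers, and TB006 levels will be determined in CSF". Footnote e adds: "The lumbar puncture procedure is optional". The same table marks a plasma PK sample at Day 36, with the note "single time point on other days" for days without serial sampling. SAP 6.4 uses Day 36 plasma, giving the Ctrough days as "Days 8, 15, 22, 29, and 36".

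**The concern.** Extent of distribution into CSF is a relative quantity: how much drug is in CSF for a given amount in plasma. A CSF concentration is penetration multiplied by plasma level. It should therefore rise with dose, and within a dose group it should vary with each patient's clearance, even if penetration is the same in everyone.

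At stake is the interpretation of one component of a Part 1 primary PK endpoint. Higher CSF levels in Group 3 than in Group 1 would be expected from dose alone and would say little about distribution. Because the puncture is optional, each dose group may supply only a few values, and raw concentrations from different doses are not on a common scale.

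**Working it through.** The documents give no figure for this endpoint to reproduce. Three checks apply.

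**1. Is the denominator collected?** Protocol Table 1 gives six plasma samples (pre-dose, end of infusion, and 1, 2, 4 and 6 hours after) on each of Days 1, 8 and 29, and one each at Day 36, Day 64, Day 104 and early discontinuation.

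3 × 6 + 4 = 22

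Protocol Table 6 also counts 22 PK collections for Part 1, so the Day 36 plasma sample is confirmed. The other lumbar puncture (Day -1) precedes dosing, so Day 36 is the only informative CSF sample.

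**2. How far could CSF concentration differ with no difference in distribution?** Write C(CSF) = R × C(plasma), with R the CSF/plasma ratio. Assume R is constant and plasma exposure is proportional to dose^b. Then CSF concentration relative to Group 1 is (dose/140)^b.

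| b (assumed) | 140 mg | 420 mg | 1,000 mg | Ratio R |
|---|---|---|---|---|
| 0.8 | 1 | 2.41 | 4.82 | 1 : 1 : 1 |
| 1.0 (dose-proportional) | 1 | 3.00 | 7.14 | 1 : 1 : 1 |
| 1.2 | 1 | 3.74 | 10.58 | 1 : 1 : 1 |

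The doses come from the documents. The exponents and constant R are assumptions; dose proportionality is itself something SAP 10.5 sets out to assess.

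**3. Is same-visit pairing close enough?** Table 1 allows ± 2 days around a visit and does not require the two Day 36 samples to be drawn at the same time. If they fell k days apart, plasma would change by 1 − 2^(−k/t½). Protocol 4.3 gives a half-life of about 10 to 12 days in monkeys and expects a longer one in humans.

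- k = 2: 1 − 2^(−2/10) = 12.9%; 1 − 2^(−2/12) = 10.9%
- k = 4: 1 − 2^(−4/10) = 24.2%; 1 − 2^(−4/12) = 20.6%

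A drift of about 11% to 24%, or less with a longer half-life, is small beside a several-fold dose effect. The ratio is usable but approximate.

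**Number of patients.** With 6 active patients per group, at most 3 × 6 = 18 can supply a pair, and fewer if some decline the puncture.

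**The case against.** The strongest reply is that little information is lost. CSF concentration is tabulated by dose, so doses are not mixed within a summary. Plasma concentration is tabulated for the same groups, and individual values of both are listed, so anyone can divide one by the other. The PK parameter list in SAP 6.4 is expressly open-ended, so adding a ratio would contradict nothing. The endpoint is descriptive, with no test or decision rule attached. The amendment rationale in Protocol Appendix 6 treats CSF data as peripheral to efficacy.

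Most of this stands, and it limits the point. A reader might infer that the plan makes it impossible to separate penetration from dose, or that raw concentration tables are the only use made of CSF data. The documents support neither. The listings allow a ratio to be formed by hand, and the graphical assessment names CSF concentration together with dose and plasma exposure. That assessment does not fill the gap, however: it names Day 29 plasma parameters rather than the Day 36 sample, and its specified axes do not include CSF concentration.

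A reader might also infer that 18 patients can simply be pooled on the ratio. Eighteen is a ceiling, and pooling presumes a similar ratio at each dose, which is part of what the endpoint should show.

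Finally, some pharmacodynamic and exploratory sections are redacted or missing from the public text, including SAP 6.5 and the opening of 10.6. The statement that no ratio is derived applies to the legible text. The endpoint sentence and the SAP 10.5 output lists are legible.

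**Conclusion.** The point holds in a limited form. The named quantity is extent of CSF distribution, while the named measure is a concentration that also carries plasma exposure. A better measure is available from samples already scheduled and is not pre-specified.

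Under dose-proportional PK and constant penetration, CSF concentration would differ about 7.1-fold from the lowest to the highest dose with no difference in distribution; the assumed range of exponents gives 4.8 to 10.6. These are illustrations, not predictions from the documents. Tabulating by dose makes the dose effect visible but does not remove it, and leaves clearance differences within a dose uncorrected.

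The consequence is modest. It concerns the reading of one descriptive component of the Part 1 PK endpoint. It should not be read as a threat to Part 2, which collects no CSF, or to dose escalation, for which Day 36 CSF is not a named input.

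**What to change.** In SAP 6.4 and 10.5, add each active patient's Day 36 CSF/plasma TB006 concentration ratio as the measure of extent of CSF distribution:

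- Use the plasma sample from the same visit and report both actual draw times.
- List the ratio and summarise it descriptively by dose group. Pool over doses only if the ratios look similar across doses.
- Add a BLQ rule. SAP 9.3 sets BLQ concentrations to zero for summary statistics, which would make the ratio zero and leave no usable geometric mean. Instead, give the number of BLQ CSF values and show each such ratio as below LLOQ divided by that patient's plasma concentration. Summarise by median and range, with a geometric mean only over quantifiable pairs and labelled as such.
- Keep CSF concentration as supporting data.

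The cost is one derived variable and one table, with no new sample or procedure. The ratio remains approximate, because the draws share a visit and not a clock time, and it will rest on few patients.

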6.5. PHARMACODYNAMIC ENDPOINTS

6.6. OTHER DRUG RELATED ENDPOINTS

Apart from above analysis, following other drug related assessment will also be performed for Part 1, secondary analysis, of the study.

- Assessment of maximum tolerable dose
- Detection of anti-TB006 antibodies (from PK plasma sampling)

7. STUDY POPULATIONS

7.1. ANALYSIS POPULATIONS

7.1.1. FULL ANALYSIS SET (FAS)

The Full Analysis Set (FAS) includes all subjects who are randomized to study drug. The FAS will be used for the analysis of disposition and protocol deviations.

7.1.2. SAFETY ANALYSIS SET (SAS)

The Safety Analysis Set (SAS) includes all subjects in the FAS who received at least one dose of study drug. Subjects in this analysis set will be analyzed according to the study drug they actually received. The FAS and the SAS will be the same if all randomized patients are dosed with study drug. The SAS will be used for all analyses, except for disposition, protocol deviations, PK and PD.

7.1.3. PHARMACOKINETIC ANALYSIS SET (PKS)

The Pharmacokinetic Analysis Set (PKS) includes all subjects who received assigned dose of TB006 and have at least one post-dose blood sample with measurable TB006 concentrations. The PKS will be used for all PK analyses.

7.1.4. PHARMACODYNAMIC ANALYSIS SET (PDS)

The Pharmacodynamic Analysis Set (PDS) includes all subjects who received assigned dose of TB006 or placebo and have at least one post-dose evaluable PD assessment. The PDS will be used for all PD and efficacy analyses.

7.1.5. EFFICACY ANALYSIS SET – PART 2 (EAS2)

The Part 2 – Efficacy Analysis Set (EAS2) includes all subjects who received assigned dose of TB006 in Part 2 and the subjects enrolled at the same TB006 dose level in Part 1, as well as all placebo patients will be included and have at least one post-dose evaluable PD assessment across subject. The EAS2 will be used for all efficacy analysis planned for Part 2 of the study.

7.2. SUBGROUPS

The dispositions, efficacy, PK/PD, biomarker, and immunogenicity analysis for Part 2 will be presented for overall and baseline patient severity: mild AD patients (MMSE 21-24) and moderate-severe AD patients (MMSE ≤ 20).

8. CHANGES IN CONDUCT OR PLANNED ANALYSES FROM THE PROTOCOL

The following analyses described in this SAP are not mentioned in the study protocol:

- Assessment of dose proportionality (see Section 10.5: Pharmacokinetics).

